# 17.1.2 Adverse Events Leading to Treatment Discontinuation

All adverse events leading to withdrawal of the subject will be recorded in the CRF and tabulated in the CSR (Table 6).

Table 6 Listing of Subjects Who Dropped Out from Study

Treatment	Subjects No.	Age (yr)	Last PK Sampling (date and actual time)	Duration	Dose	Concomitant Medication	Reason for Discontinuation
			yyyy-mm-dd, hh:mm	yyyy-mm-dd, hh:mm (dd,hh,mm)			
						·	

Test drug: Glucophage® XR (PT Merck Tbk, Indonesia) Comparator drug: Glucophage® XR (Merck Sante, France)

# 17.2 Deaths, Other Serious Adverse Events, and Other Significant Adverse Events

#### 17.2.1 **Deaths**

All serious adverse events that may result in death will be recorded in the SAE form and attached to the CRF. The summary of death cases will be tabulated in the CSR (Table 7).

Table 7 Listing of Deaths During the Study

Period (Treatment)	Subject No.	Serious Adverse Event	Date and Time of Death	Comments			
Test drug: Glucophage® XR (PT Merck Tbk, Indonesia)							

Test drug: Glucophage® XR (PT Merck Tbk, Indonesia) Comparator drug: Glucophage® XR (Merck Sante, France)

#### 17.2.2 Serious Adverse Events

All serious adverse events will be recorded in the SAE form and attached to the CRF. The summary of serious adverse events will be tabulated in the CSR (Table 8).

**Table 8** Listing of Serious Adverse Events

Period (Treatment)	Subject No.	Serious Adverse Event	Start Date (yyyy,mm,dd, hh:mm)	End Date (yyyy,mm,dd, hh:mm)	Intensity	Causality	Time of drug Administration	Withdrawal/ Drop-out	Outcome (observed until FU visit)

Test drug: Glucophage® XR (PT Merck Tbk, Indonesia) Comparator drug: Glucophage® XR (Merck Sante, France)

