7.4 Follow-Up Visit

Follow-up procedures will be performed after the last study activity in the second dosing period, and completed within 7 days after the last blood sampling. Procedures will include physical examination, assessment of vital signs (blood pressure, pulse rate, respiratory rate and temperature), body measurements (height and weight), ECG, clinical laboratory tests (liver function, renal function, blood glucose, hematology, urinalysis), and adverse event evaluation.

If a subject who has received at least one dose of the study drug withdraws prematurely, the Follow-Up Visit will need to be completed within 7 days after his/her last blood sampling.

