Definition of the Adverse Event Reporting Period

The AE reporting period for safety surveillance begins when the subject is initially included in the study (date of first signature on the informed consent form [ICF]) and continues until the last post-treatment safety visit, which in this case is completion of the Follow-Up Visit.

Any SAE assessed as related to metformin hydrochloride (Glucophage® XR) must be reported whenever occurs, irrespective of the time elapsed since the last administration of metformin hydrochloride (Glucophage® XR).

Procedure for Reporting Serious Adverse Events

In the event of any new SAE occurring during the reporting period, the Investigator must immediately (within a maximum of 24 hours after becoming aware of the event) inform the Sponsor in writing. All written reports should be transmitted using Merck SAE Report Form, which must be completed by the Investigator following specific completion instructions.

In exceptional circumstances, an SAE (or follow-up information) may be reported by telephone; in these cases, a written report must be sent immediately thereafter by e-mail to [contact].

Relevant pages from the CRF may be provided in parallel (for example, medical history, concomitant drugs). Additional documents may be provided by the Investigator, if available (for example, laboratory results, hospital report, autopsy report). In all cases, the information provided on the SAE Report Form must be consistent with the data about the event recorded in the CRF.

The Investigator must respond to any request for follow-up information (for example, additional information, outcome, final evaluation, other records where needed) or to any question the Sponsor may have on the AE within the same timelines as those noted above for initial reports. This is necessary to ensure prompt assessment of the event by the Sponsor to allow the Sponsor to meet strict regulatory timelines associated with expedited safety and tolerability endpoints reporting obligations.

Merck Global Drug Safety department may contact the Investigator to obtain further information or to discuss the event.

Safety Reporting to Local Health Authority, Ethics Committee and Investigator

The Sponsor will send appropriate safety notifications to the local Health Authority, *Badan Pengawas Obat dan Makanan* (BPOM) in accordance with applicable laws and regulations.

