The Investigator must comply with any applicable site-specific requirements related to the reporting of SAEs (particularly deaths) involving trial subjects to the Ethics Committee that approved the study.

In accordance with ICH GCP, the Sponsor will inform the Investigator of "findings that could adversely affect the safety of subjects, impact the conduct of the trial or alter the IEC's/IRB's approval/favorable opinion to continue the trial." In particular and in line with respective regulations, the Sponsor will inform the Investigator of AEs that are both serious

and unexpected and are considered to be related to the administered drugs ("suspected unexpected serious adverse reactions" or SUSARs). The Investigator should place copies of Safety Reports in the Investigator Site File. BPOM regulations with regard to Safety Report notifications to Investigators will be taken into account.

The Investigator will be responsible for promptly notifying the concerned Ethics Committee of any Safety Reports provided by the Sponsor and of filing copies of all related correspondence in the Investigator Site File.

Monitoring of Subjects with Adverse Events

AEs are recorded and assessed continuously throughout the study and are assessed for final outcome at the Follow-up Visit. All SAEs ongoing at the Follow-up Visit must be monitored and followed up by the Investigator until stabilization or until the outcome is known, unless the subject is documented as "lost to follow-up". Reasonable attempts to obtain this information must be made and documented. It is also the responsibility of the Investigator to ensure that any necessary additional therapeutic measures and follow-up procedures are performed.

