12.1.3 Vital Signs, Physical Examinations, ECG and Other Assessments

Vital sign including blood pressure, pulse rate, and respiratory rate will be measured during Screening Visit, during blood sampling per schedule listed in Appendix B Study Flow Chart, and during the Follow-Up Visit. Physical examination, body measurement (height and weight), and ECG will be performed during Screening and Follow-Up visit.

A full standard 12-lead ECG (I, II, III, aVR, aVL, aVF, V1-V6) for about 5 seconds (at least 4 adjacent beats, calibration: 25 mm/sec 10 mm/mV) will recorded in the CRF. The 12-lead ECG will be analyzed, assessed for plausibility and clinical relevance and signed by the Investigator.

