# 17.1.1 All Adverse Events

All of adverse events occurred during the study will be listed in the CSR (Table 3). An overview of all adverse events will be presented in Table 4. Adverse reaction (from test and comparator drug) would be categorized as unrelated, unlikely, possibly related, probably, and definite related based on literature data and pharmacokinetics profile (Table 5). All adverse events, regardless of severity, will be followed up and recorded by the investigator. All adverse events will be recorded in the CRF and tabulated in the CSR.

Table 3 List of Adverse Events Occurred

	Listing All Adverse Events											
Period (I or II) Treatment	Subject No.	System Organ Class/ Preferred Term/ Reported Term	Serious criteria	Start Date	End Date (AE Duration)	Severity	Relationship to IMP	Action taken with study treatment	Other action taken	Outcome	Comment	
Period I Reference		/ / 	No	yyyy-mm-dd, hh:mm	yyyy-mm-dd, hh mm (dd,hh,mm)							
Period 2 Test												

Table 4 Overview of all Adverse Events (by Group and Overall)

	Test Drug (N=xx)	Comparator Drug (N=xx)	All (N=xx)
Subjects with any AE (%)	0 (00.0%)	0 (00.0%)	0 (00.0%)
Number of all AEs	0	0	0
Number of treatment emergent AEs	0	0	0
Drug-related AEs	0	0	0
Serious AEs	0	0	0
Withdrawal due to AEs	0	0	0

**Table 5** Adverse Events: Number Observed

Adverse event	vent Mild		Moderate			Severe				Total						
	Definite	Probably	Possibly	Unlikely	Unrelated	Definite	Probably	Possibly	Unlikely	Unrelated	Definite	Probably	Possibly	Unlikely	Unrelated	
Test Drug																
SOC 1																
	0	0	0	0	0	0	0	0	0	0	0	0	0	0	0	0 (0.0%)
SOC 2																
•••	0	0	0	0	0	0	0	0	0	0	0	0	0	0	0	0 (0.0%)
SOC 3																
•••	0	0	0	0	0	0	0	0	0	0	0	0	0	0	0	0 (0.0%)
Others																
•••	0	0	0	0	0	0	0	0	0	0	0	0	0	0	0	0 (0.0%)
Comparator Drug																
SOC 1																
•••	0	0	0	0	0	0	0	0	0	0	0	0	0	0	0	0 (0.0%)
SOC 2																
•••	0	0	0	0	0	0	0	0	0	0	0	0	0	0	0	0 (0.0%)
SOC 3																
•••	0	0	0	0	0	0	0	0	0	0	0	0	0	0	0	0 (0.0%)
Others																
	0	0	0	0	0	0	0	0	0	0	0	0	0	0	0	0 (0.0%)

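### SAP Table 8 stops the SAE outcome at the Follow-Up Visit, although the protocol follows ongoing SAEs beyond it

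*SAP*

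**What the plan says.** **SAP.** Section 17.2.2 plans a listing of serious adverse events, Table 8. Its last column is headed "Outcome (observed until FU visit". The End Date column of the same table has no such limit. Table 3 (section 17.1.1) lists all adverse events, with a column for serious criteria and with End Date and Outcome columns, again without a limit. Table 7 (section 17.2.1) lists deaths during the study, with date and time of death.

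**Protocol.** Section 12.1, under the monitoring of subjects with adverse events, states: "All SAEs ongoing at the Follow-up Visit must be monitored and followed up by the Investigator until stabilization or until the outcome is known". The exception is a subject documented as lost to follow-up. The same section requires any SAE judged related to metformin to be reported, "irrespective of the time elapsed since the last administration of metformin hydrochloride". The sponsor's SAE form in Appendix B can be marked as an initial or a follow-up report. Its outcome choices are unknown, fatal, ongoing, and resolved with or without sequelae.

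**Timing.** Under protocol section 7.4, follow-up procedures come after the last activity of the second dosing period and are "completed within 7 days after the last blood sampling". The last sample is taken 32 hours after dosing.

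**The concern.** The protocol obliges the site to collect SAE outcomes after the Follow-Up Visit, but the table dedicated to SAEs is headed so that those outcomes are left out. An SAE that is ongoing at the visit and later resolves, leaves sequelae or proves fatal would stand in Table 8 with its status on the visit day. A related SAE that begins after the visit has no valid entry in that column at all.

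Safety and tolerability are a secondary objective, and an SAE listing is read case by case. With 48 healthy volunteers few SAEs are to be expected, so what is at stake is the correctness of a single case and not a rate or a comparison.

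**Working it through.** The plan gives no figure to reproduce. The check is one piece of arithmetic and a comparison of texts.

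**1. How early the cut-off falls.** Inputs: last PK sample at 32 h (protocol 7.3 and 9.1); Follow-Up completed within 7 days of the last sample (protocol 7.4).

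- Latest visit = 32 h + 7 × 24 h = 32 + 168 = 200 h after the last dose.
- 200 / 24 = 8.3 days.
- Earliest visit for a subject completing both periods: directly after the 32 h sample, because no minimum interval is stated.

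For an SAE that starts after the second dose, Table 8 as headed therefore reflects at most 200 h of observation, and less if the event starts later or the visit is early.

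**2. Where an SAE outcome is recorded, and up to when.**

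| Place | Item | Limit stated |
|---|---|---|
| Protocol 12.1 | Follow-up of ongoing SAEs | Stabilisation or known outcome, unless lost to follow-up |
| Protocol 12.1 | Reporting of related SAEs | None |
| Protocol Appendix B, SAE form | Outcome, with follow-up reports | None |
| SAP Table 3 | End Date and Outcome | None |
| SAP Table 8 | End Date | None |
| SAP Table 8 | Outcome | Follow-Up Visit |
| SAP Table 7 | Date and time of death | No visit limit, but titled as deaths during the study |

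The Table 8 outcome column is the only item tied to the visit.

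**3. What happens to one case.** Take an SAE that starts after the second dose, is ongoing at Follow-Up and resolves with sequelae afterwards.

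- SAE form, follow-up report: resolved with sequelae.
- Table 3: end date after the visit; outcome resolved with sequelae.
- Table 8: the same end date, but the outcome still ongoing.

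The Table 8 row contradicts itself, and it contradicts two other records of the same event. If the event is fatal after the visit, Table 8 again shows it as ongoing. Whether the death enters Table 7 depends on how its title is read.

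**The case against.** **The later outcome is not lost.** A reader might infer from Table 8 that the clinical study report would never show what became of an SAE after the visit. Table 3 answers that: its serious-criteria column shows that SAEs belong in it, and its outcome is not cut. The SAE form also takes follow-up reports. This objection stands. It reduces the point to an inconsistent column in one listing.

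**It is not an undeclared change of analysis.** SAP section 9 declares no changes, and one could hold that against Table 8. But section 9 speaks of statistical methods and planned analyses, while the protocol text sets a monitoring duty for the investigator and prescribes no listing. A table heading does not alter how subjects are followed. This stands too.

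**Non-serious events.** A stronger reading is tempting here. Hematology and blood chemistry are scheduled only at Screening and Follow-Up, and for the ECG the protocol says "and ECG will be performed during Screening and Follow-Up visit". A post-dose change in these may thus first be seen at Follow-Up. The protocol also says "AEs are recorded and assessed continuously throughout the study and are assessed for final outcome at the Follow-up Visit", and its AE reporting period "continues until the last post-treatment safety visit, which in this case is completion of the Follow-Up Visit". A reader might conclude that such events are closed on the day they are found, carry no duty of follow-up, or fall outside the AE period. The documents do not support this:

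- Assessing an outcome at a visit does not close the event, and the AE form in protocol Appendix A offers a not-resolved outcome.
- SAP section 17.1.1 states: "All adverse events, regardless of severity, will be followed up and recorded by the investigator".
- The footnote to SAP Table 9 foresees repeat measurement of clinically relevant deviations, and Table 11 has an Outcome column for unscheduled measurements.
- Protocol 12.1 makes the investigator responsible for any further follow-up procedures that are needed. It sets no time limit and does not expressly confine this to SAEs.
- An abnormality in a sample or ECG taken at the visit exists during the visit, whenever the result is read.
- Under protocol 12.1 an abnormal finding is an AE only if it comes with signs or symptoms, leads to discontinuation, or is judged medically important.

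What remains is that the two documents word the follow-up of non-serious events differently and neither gives an end point. That calls for a clarification and is not a demonstrated error.

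**Conclusion.** The heading of the Table 8 outcome column conflicts with the SAE follow-up and reporting rules of protocol section 12.1 and should be corrected. Applied literally, it can put a superseded outcome into the dedicated SAE listing for any SAE still ongoing at a visit held no later than 200 h (8.3 days) after the last dose.

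The severity is minor. One column of one listing is affected, the data are already required, the correct outcome can appear in Table 3 and on the SAE form, and the bioequivalence analysis is untouched. The conclusion assumes that the heading would be followed as written, and it has practical effect only if an SAE is ongoing at the visit or begins after it. It does not extend to non-serious events.

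**What to change.** In SAP section 17.2.2, change the Table 8 column heading to *Latest known outcome (with date) at database lock*. In sections 17.2.1 and 17.2.2, add one sentence stating that deaths and SAEs reported after the Follow-Up Visit and before database lock are included in Tables 7 and 8.

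Two small clarifications could be made at the same time. The wording on non-serious events in protocol 12.1 and SAP 17.1.1 should be reconciled. The Table 9 footnote should cite Table 11, which lists unscheduled measurements, instead of Table 10, which lists vital signs.

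The cost is one heading, one sentence and a corrected cross-reference, plus the wording of the reconciliation. The only running cost is an occasional late outcome query before lock. No new data are needed for the SAE listing.

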# 17.3 Clinical Laboratory Evaluation

All clinical laboratory results will be recorded in the CRF and tabulated in the CSR. Baseline clinical laboratory test results will be presented alongside vital signs measurements, ECG findings, and physical examination performed during Screening in Table 9 (see Section 13.3). Clinical laboratory test results and other characteristics during Follow-Up Visit will be presented as shown (Table 9).

Table 9 Clinical Laboratory Test and ECG of Subjects During Follow-Up Visit

Parameter	Unit		Normal Values			
			(Init	tials)		
		(SUBJECT ID)	(SUBJECT ID)	(SUBJECT ID)	(SUBJECT ID)	
		(INITIAL)	(INITIAL)	(INITIAL)	(INITIAL)	
		(GENDER)	(GENDER)	(GENDER)	(GENDER)	
Hematology Leucocyte Erythrocyte Hb Hematocrit Thrombocyte Blood Chemistry	x 10  /μL x 10  /μL g/dL % x 10  /μL					M :3.8 - 10.6 F: 3.6 - 11.0 M :4.4 - 5.9 F: 3.8 - 5.2 M:13.2 - 17.3 F: 11.7 - 15.5 M :40 - 52 F: 35 - 47 150 - 440
Total bilirubin Direct bilirubin AST ALT AP Albumin Total protein Blood glucose Ureum Creatinine	mg/dL mg/dL IU/L IU/L IU/L g/dL g/dL mg/dL mg/dL mg/dL					<1.2 <0.50 M: <35 F: <31 M: <45 F:<34 M: 53 - 128 F: 42 - 98 3.5 - 5.2 6.4 - 8.3 <140 13 - 43 M: 0.67 - 1.17 F: 0.51 - 0.95
Urinalysis Clarity Color Glucose Bilirubin Ketone Specific Gravity Blood pH Protein Urobilinogen Nitrite Leucocyte Sediment:	EU/dL					Clear Yellow Neg. Neg. Neg. 1.015 - 1.025 Neg. 5 - 8 Neg. 0.2 - 1.0 Neg. Neg.
- RBC - WBC - cast - epithel: squamous transitional tubular - crystal - bacteria  ECG Conclusion	cells/HPF cells/HPF					0 - 2 0 - 5 Neg. Neg./ Pos. Neg./ Pos. Neg./ Pos. Neg./ Pos. Neg./ Pos. Neg. for male  Normal Sinus Rhythm

\*deviate from normal values, not clinically significant \*\* clinically relevant deviation for repeated measurement please refer to Table 10 unscheduled measurements

# 17.4 Vital Signs

Vital signs will be recorded in the CRF and tabulated in the CSR (Table 10).

**Table 10** Vital Signs Monitoring

Subject No.	Period	Vital Signs	Screening	Day 1		Day 2		Follow				
				Pre-dose	2h	4h	6h	8h	12h	24h	32h	-Up
S1	1	Systolic BP (mmHg)										
		Diastolic BP (mmHg)										
		Pulse rate (beats/min)										
		Respiratory rate (times/min)										
	2	Systolic BP (mmHg)										
		Diastolic BP (mmHg)										
		Pulse rate (beats/min)										
		Respiratory rate (times/min)										
S2	1	Systolic BP (mmHg)										
		Diastolic BP (mmHg)										
		Pulse rate (beats/min)										
		Respiratory rate (times/min)										
	2	Systolic BP (mmHg)										
		Diastolic BP (mmHg)										
		Pulse rate (beats/min)										
		Respiratory rate (times/min)										

Unscheduled measurements will be listed in Table 11.

**Table 11** Unscheduled Measurement

Subject No.	Parameter	Result	Outcome		

# 17.5 Other Safety or Tolerability Evaluations

Not applicable

#### 18 Benefit Risk Assessment

Not applicable.

